In addition, the responder endpoint will be analyzed by a generalized linear mixed model (GLMM) with treatment, visit, country, sex, and treatment by visit interaction as fixed effects. Visit ordering will be treated as a repeated measure within subjects. The GLMM model will use all available cough frequency data on Day 28, 56, and 84. The least-squares (LS) mean proportions with the associated standard errors will be displayed for each treatment group. Estimated odds ratio (serlopitant vs. placebo) along with corresponding one-sided 95% CIs and p-values will also be presented at each post-baseline timepoint.

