  TABLES COUNTRY* SEX* TRT01PN* CRIT1FN/CMH  
          alpha=0.1 ;  
  weight Count;  
run;
```

```
/*Estimate difference in proportions (Serlopitant - Placebo) by Country*/  
PROC FREQ DATA=ADCF;  
  TABLES COUNTRY* TRT01PN* CRIT1FN/ riskdiff (cl= MN CORRECT)  
          alpha=0.1 ;  
  weight Count;  
run;
```

```
/*Estimate difference in proportions (Serlopitant - Placebo) by Sex*/  
PROC FREQ DATA=ADCF;  
  TABLES SEX* TRT01PN* CRIT1FN/ riskdiff (cl= MN CORRECT)  
          alpha=0.1 ;  
  weight Count;  
run;
```

```
/*Estimate difference in proportions (Serlopitant - Placebo) by Country and by  
Sex*/  
PROC FREQ DATA=ADCF;  
  TABLES COUNTRY* SEX* TRT01PN* CRIT1FN/ riskdiff (cl= MN CORRECT)  
          alpha=0.1 ;  
  weight Count;  
run;
```

A sample of the SAS code for GLMM analysis is provided as below:

```
PROC SORT DATA=ADAMDATA.ADCF OUT=ADCF;  
BY USUBJID AVISITN;  
WHERE PARAMCD=' XXXXX' AND DTYPE='' AND AVISITN>0;  
RUN;
```

```
PROC GLIMMIX DATA=ADCF;  
CLASS TRT01PN USUBJID AVISITN COUNTRY SEX;  
MODEL CRIT1FN (EVENT='1') = TRT01PN AVISITN TRT01PN*AVISITN COUNTRY  
/ LINK=LOGIT DIST=BINARY ODDSRATIO (DIFF=FIRST);
```

```
RANDOM _RESIDUAL_ / SUBJECT=USUBJID (TRT01PN) TYPE=UN;

/*LS-mean estimates and SEs for proportions Serlopitant vs. placebo*/
LSMEANS TRT01PN*AVISITN / ILINK CL ;

/*Estimates of odds ratio (Serlopitant vs. placebo) and CI at each post-
baseline visit*/
ESTIMATE 'TRT 5mg / P' TRT01PN -1 1,

      'TRT 5mg / P ON DAY 28' TRT01PN -1 1
              TRT01PN*AVISITN -1 0 0 1,
      'TRT 5mg / P ON DAY 56' TRT01PN -1 1
              TRT01PN*AVISITN 0 -1 0 0 1,
      'TRT 5mg / P ON DAY 84' TRT01PN -1 1
              TRT01PN*AVISITN 0 0 -1 0 0 1 / EXP CL UPPER UPPERTAILED;

RUN;
```

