## APPENDIX C: STUDY VISIT MAP WITH MATCHED INTERVAL ID

## Study Visits and Matched Interval IDs in Datasets

Study Procedures	Screening	Baseline	Treatment Period						Follow-up	
	Screening	Day 0 Study Day -1	Day 1	Day 14	Day 28	Day 56	Day 84	Day 85 /ETD	Day 112	Day 113
VISITNUM	1	2	3	4	5	6	7	8	9	10
Interval ID	148	149	150	151	155	156	157	158	159	160
Study Visit Window			1 ST DAY DOSING	± 3	± 3	± 3	± 3	± 3	± 3	± 3
Vital Sign Data a	X	X	X		X	X	X	X		X
Cough Severity VAS Monitoring Data a	X	X			X	X	X	X	X	X
Telephone Contact Data a				X						
Cough Monitoring Data b		X			X	X	X		X	

a Data collected at visits marked as X. Visit dates will be derived based on the following three datasets: vital sign, cough severity VAS monitoring, and telephone contact. If there is any discrepancy in a visit date, the date recorded in vital sign dataset will be considered as the primary date.

b The cough monitoring data has regular visits labeled as Baseline, Day28, Day56, Day84, and Day112, and the repeated visits labeled as Baseline-R, Day28-R, Day56-R, Day84-R and Day112-R. Both regular and repeated records at the specific visit will be included in analysis data. Repeated evaluations are usually due to equipment failures or unacceptable initial evaluations.

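### The SAP's sample code for the supporting responder estimates (H3/H4) departs from the SAP text: sex is left out of the GLMM, the visit filter does not enforce Days 28/56/84, and no pooled stratified M&N difference is requested

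*SAP*

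**What the plan says.** **GLMM, text.** SAP 9.6.3.2 says that the responder endpoint will also be "analyzed by a generalized linear mixed model (GLMM) with treatment, visit, country, sex, and treatment by visit interaction as fixed effects". On the data it says: "The GLMM model will use all available cough frequency data on Day 28, 56, and 84". Odds ratios are to be reported at each post-baseline timepoint.

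**GLMM, code.** SAP Appendix A selects the records with "WHERE PARAMCD=' XXXXX' AND DTYPE='' AND AVISITN>0". It declares "CLASS TRT01PN USUBJID AVISITN COUNTRY SEX" and then fits "MODEL CRIT1FN (EVENT='1') = TRT01PN AVISITN TRT01PN*AVISITN COUNTRY". One overall ESTIMATE row and three by-visit rows follow.

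**M&N, text.** Protocol 8.9.3 and its Table 2 name the stratified M&N method, adjusted for gender and country, for both responder endpoints. SAP 8.1 and 9.6.3.2 call for a treatment difference estimated by stratified M&N; 8.1 gives the strata as country and sex.

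**M&N, code.** Three PROC FREQ blocks are commented as running by country, by sex, and by country and sex. The last uses "TABLES COUNTRY* SEX* TRT01PN* CRIT1FN/ riskdiff (cl= MN CORRECT"). All three set alpha to 0.1.

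**Primary comparison of response rates.** SAP 9.6.3.2 assigns this to the CMH test stratified by country and sex.

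**The concern.** The text and the code of one SAP describe different analyses, and a programmer who starts from the code would not produce what the text promises.

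Sex is a stratification factor and should be in the model as stated. The GLMM filter has no upper visit limit, although cough is also recorded at Day 112, after treatment has ended, and the by-visit contrasts are written for exactly three visits. The M&N steps yield several stratum-level differences where the text asks for one stratified difference.

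At stake are the supporting odds ratios and the risk difference that would be reported beside H3 and H4 in the SAP 8.7 hierarchy.

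**Working it through.** No figure stated in the plan depends on this point, so the check sets text against code. One numerical illustration on assumed counts follows.

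**1. Sex.** The text lists five fixed effects: treatment, visit, country, sex and treatment-by-visit. The MODEL statement has four: treatment, visit, treatment-by-visit and country. Sex is declared in CLASS and never used. The MMRM code in the same appendix has sex in both statements, so this looks like a slip and not a choice.

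**2. Visits.** Inputs:

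- The SAP Appendix C map numbers Baseline 2, Days 28/56/84 as 5/6/7, and Day 112 as 9. Its footnote b says: "The cough monitoring data has regular visits labeled as Baseline, Day28, Day56, Day84, and Day112".
- The map's variable is VISITNUM, not AVISITN. However, the rank-analysis code reads ADCF, the dataset that the GLMM also reads, and selects Week 12 with `AVISIT=7`. The multiple-imputation code comments likewise refer to visits 5, 6 and 7.
- SAP 7.3 makes Day 112 an analysis visit for cough frequency, beginning after the earlier of Day 91 and seven days past the last dose.

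On this numbering, `AVISITN>0` keeps Day 112 if that record carries a responder value.

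The ESTIMATE rows give treatment coefficients (-1, +1), none for visit, and up to six treatment-by-visit coefficients, ordered as placebo visits and then serlopitant visits. Such a row is estimable only if the interaction coefficients sum to -1 over placebo visits, to +1 over serlopitant visits, and to 0 over the two arms at each visit.

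| Row label | Three visits (28, 56, 84) | Four visits (28, 56, 84, 112) | Condition that fails with four |
|---|---|---|---|
| Day 28 | -1 placebo D28, +1 serlopitant D28 | -1 placebo D28, +1 placebo D112 | placebo sum is 0, not -1 |
| Day 56 | -1 placebo D56, +1 serlopitant D56 | -1 placebo D56, +1 serlopitant D28 | Day 28 sums to +1, Day 56 to -1 |
| Day 84 | -1 placebo D84, +1 serlopitant D84 | -1 placebo D84, +1 serlopitant D56 | Day 56 sums to +1, Day 84 to -1 |

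Building the design matrix X and testing whether L = L X⁻X for each row L gives the same answer: all three rows are estimable with three visits and none with four. The overall row names only treatment, so it would still run. If the visits are weighted equally, Day 112 would be 1 of 4 visits, or 25% of that contrast.

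**3. M&N.** The three blocks tabulate treatment by response within country, within sex, and within each country-by-sex cell. The code comments describe the output in those terms, and no block asks for a common difference.

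Illustration, with assumptions that are not in the documents beyond the enrolment and dropout figures:

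- Evaluable per arm: 85 × (1 - 0.15) = 72.25, taken as 72.
- Cells per arm: 26 women and 10 men in each of two countries, 2 × (26 + 10) = 72.
- Responders: 13/26 against 8/26 in women, 5/10 against 3/10 in men.
- Stratum weights n₁n₂/(n₁ + n₂): 13 for women and 5 for men in each country, total 36.
- Pooled difference: (26/36) × (13/26 - 8/26) + (10/36) × (5/10 - 3/10) = 0.139 + 0.056 = 0.194.

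| Estimate | Difference | 90% M&N interval |
|---|---|---|
| Women, each country | 0.192 | -0.034 to 0.400 |
| Men, each country | 0.200 | -0.166 to 0.519 |
| Pooled over the four cells | 0.194 | 0.058 to 0.324 |

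The documents give no country or sex split for this trial. With 70/30 splits on both factors, the smallest cell would hold 72 × 0.3 × 0.3 = 6.5 subjects per arm instead of 10. Cell intervals therefore cannot stand in for the pooled one.

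**The case against.** The strongest reply is that nothing confirmatory depends on this code. The SAP makes the stratified CMH its primary comparison of response rates. The CMH code is stratified by country and sex and limited to a single visit. The GLMM is an added analysis, and in SAP 9.6.3.2 the M&N method serves for estimation. The code is labelled a sample and contains placeholders, and a programmer who follows the text would run the right analyses. This stands, and it limits the weight of the point. It does not remove the contradiction.

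The second reply concerns visit coding. The note under the MMRM code describes AVISITN as Days 28, 56 and 84 only, and on that reading every contrast is correct. Moreover, under the Appendix C numbers a filter of `>0` would exclude nothing, which suggests that its author had another coding in mind. Part of this stands: the Day 112 problem is conditional. But that note explains code reading a different dataset (LOGEFF), and the GLMM filter sets no upper limit. The code does not itself enforce the restriction in the text.

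Three stronger readings are tempting and are not supported:

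- *The Day 84 odds ratio would silently compare different visits.* The misaligned rows are non-estimable, so they should appear as missing results, not as a plausible wrong number.
- *Baseline rows certainly enter as well.* The coding of Baseline in AVISITN is not stated, and a response defined by change from baseline need not exist at Baseline.
- *The H3/H4 p-values are wrong.* They come from the CMH test under the SAP.

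That PROC FREQ does not pool unless asked is software behaviour and not in the documents. The comments in the code point the same way.

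**Conclusion.** The sample code contradicts the SAP text in three places, with different degrees of certainty.

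- The omission of sex from the GLMM is certain on the face of the code.
- The missing request for a common M&N difference is clear from the three blocks and their comments. It matters most of the three, because the Protocol names that method for both responder endpoints.
- The unbounded visit filter is certain. Its consequence (Day 112 admitted, three non-estimable by-visit rows, an overall odds ratio diluted by an off-drug visit) holds if AVISITN follows the Appendix C map and Day 112 carries a responder value. The other sample code makes this numbering likely; the documents do not state it.

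The damage is confined to the supporting odds ratio and the stratified risk-difference estimate. The CMH test of H3 and H4 is unaffected, and so is the testing hierarchy. Whether M&N or CMH should be the formal test is a separate question. The interval widths above illustrate scale on assumed counts and predict nothing for this trial.

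**What to change.** Make three edits to SAP Appendix A before database lock:

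1. Add SEX to the GLMM MODEL statement.
2. Replace the open-ended filter with an explicit restriction to the Day 28, Day 56 and Day 84 analysis visits. First confirm their AVISITN codes in the analysis dataset specification, and state those codes in the appendix. Do not hard-code 5, 6 and 7 on the strength of the VISITNUM map alone.
3. Request the common stratified M&N risk difference over country by sex, with 90% limits to match the alpha of 0.1 already coded. Keep the by-country and by-sex runs as descriptive output.

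The cost is a few lines of code and a short check of the visit codes. No new data are needed, and no endpoint, test or stated sample size changes.

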**A sample of the SAS code for sensitivity analysis using the copy-reference MI method is provided as below:**

```
/*Generate transpose of adcf - wide format before Step 1*/
/*----- Generates 10 imputed data sets based on original (non-transformed)
data-----*/
/*Step 1: Achieve Monotone Missing Data Pattern */
PROC MI DATA=&DATA SEED=14823 NIMPUTE=10 OUT=MONO;
  /* Use numeric TRT01PN */
  VAR BASE AVAL1 AVAL2 AVAL3; /*Refer to AVAL at Visits 5, 6, and 7*/
  MCMC IMPUTE=MONOTONE NBITER=5000 NITER =5000;
  BY TRT01PN;
run;

/*Step 2: Achieve Control-Based Copy-Reference Imputation */

PROC MI DATA=MONO SEED=14823 NIMPUTE=1 OUT=OUTM1;
  CLASS TRT01PN;
  By _IMPUTATION_;
  VAR TRT01PN BASE AVAL1 AVAL2 AVAL3;
  MONOTONE REG (AVAL2 AVAL3);
  MNAR MODEL (AVAL1 AVAL2 AVAL3/ MODELOBS = (TRT01PN = '0'));
  /*Control=Placebo*/
RUN;
PROC SORT DATA =OUTM1; BY _IMPUTATION_ TRT01PN USUBJID LBASE; RUN;
/*Generate transpose of OUTM1 - skinny format before Step 3*/

/*Step 3: Run MMRM Analysis on Imputed Data */

PROC MIXED DATA=OUTM1 METHOD=REML;
  BY _IMPUTATION_;
  CLASS TRT01PN USUBJID AVISITN COUNTRY SEX;
```

```

MODEL LCHG = TRT01PN AVISITN COUNTRY SEX TRT01PN*AVISITN LBASE / DDFM=KR;
/*LCHG AND LBASE ARE BASED ON THE LOG-TRANSFORMED COUGH FREQUENCY*/
REPEATED / SUBJECT=USUBJID (TRT01PN) TYPE=UN;
LSMEANS TRT01PN*AVISITN / CL DIFF PDIFF;
  ESTIMATE 'TRT S - P ON DAY 28' TRT01PN -1 1
            TRT01PN*AVISITN -1 0 0 1 / CL LOWER LOWERTAILED;
  ESTIMATE 'TRT S - P ON DAY 56' TRT01PN -1 1
            TRT01PN*AVISITN 0 -1 0 0 1 / CL LOWER LOWERTAILED;
  ESTIMATE 'TRT S - P ON DAY 84' TRT01PN -1 1
            TRT01PN*AVISITN 0 0 -1 0 0 1 / CL LOWER LOWERTAILED;
ODS OUTPUT PARAMETERESTIMATES=PESTIMATES;
RUN;
```

```

/*Step 4: Combining estimates from each imputed data set */
/*First, sort the data of estimates by visit (variable "LABEL") */
PROC MIANALYZE DATA=PESTIMATES;
  MODELEFFECTS ESTIMATE;
  STDERR STDERR;
  BY LABEL;
  ODS OUTPUT PARAMETERESTIMATES= MIPARM;
RUN;
```

A sample of the SAS code for sensitivity analysis using the tipping-point approach is provided as below:

```

/*-----*/
/*--- Performs multiple imputation analysis ---*/
/*--- for specified shift parameters: ---*/
/*--- data= input data set ---*/
/*--- smin= min shift parameter ---*/
/*--- smax= max shift parameter ---*/
/*--- sinc= increment of the shift parameter ---*/
/*--- outparms= output parameters ---*/
/*-----*/

%MACRO MIPARMS( DATA=, SMIN=, SMAX=, SINC=, OUTPARMS=);

DATA &OUTPARMS;
  SET _NULL_;
RUN;

/*----- # of shift values -----*/
%LET NCASE= %SYSEVALF( (&SMAX-&SMIN)/&SINC, CEIL );

/*---- Multiple imputation analysis for each shift ----*/
%DO JC=0 %TO &NCASE;
  %LET SJ= %SYSEVALF( &SMIN + &JC * &SINC);

  /*---- Generates 10 imputed data sets ----*/
```

```
/*Step 1: Achieve Monotone Missing Data Pattern */
PROC MI DATA=&DATA SEED=14823 NIMPUTE=10 OUT=MONO;
  ** Use numeric TRT01PN ;
  VAR BASE AVAL1 AVAL2 AVAL3; /*Refer to AVAL at Visits 5, 6, and 7*/
  MCMC IMPUTE=MONOTONE NBITER=5000 NITER =5000;
  BY TRT01PN;
run;

/*Step 2: Impute all visits under MAR first, then apply delta adjustments at
each visit*/
PROC MI DATA=OUTM1 SEED=14823 NIMPUTE=1 OUT=OUTM2;
  CLASS TRT01PN;
  BY _IMPUTATION_;
  VAR TRT01PN BASE AVAL1 AVAL2 AVAL3;
  MONOTONE REG (AVAL2 AVAL3);
  MNAR ADJUST( AVAL1 / SHIFT=&SJ ADJUSTOBS=(TRT01PN ='1') );
  MNAR ADJUST( AVAL2 / SHIFT=&SJ ADJUSTOBS=(TRT01PN ='1') );
  MNAR ADJUST( AVAL3 / SHIFT=&SJ ADJUSTOBS=(TRT01PN ='1') );
  RUN;
  PROC SORT DATA =OUTM1; BY _IMPUTATION_ TRT01PN USUBJID BASE; RUN;
/*Generate transpose of OUTM2 - skinny format before Step 3*/

/*Step 3: Run MMRM Analysis on Imputed Data */

PROC MIXED DATA=OUTM2 METHOD=REML;
  BY _IMPUTATION_;
  CLASS TRT01PN USUBJID AVISITN COUNTRY SEX;
  MODEL LCHG = TRT01PN AVISITN COUNTRY SEX TRT01PN*AVISITN LBASE /
  DDFM=KR; /*CHG AND BASE ARE BASED ON THE LOG-TRANSFORMED COUGH
FREQUENCY*/
  REPEATED / SUBJECT=USUBJID (TRT01PN) TYPE=UN;
  LSMEANS TRT01PN*AVISITN / CL DIFF PDIFF;
  ESTIMATE 'TRT S - P ON DAY 28' TRT01PN -1 1
           TRT01PN*AVISITN -1 0 0 1 / CL LOWER LOWERTAILED;
  ESTIMATE 'TRT S - P ON DAY 56' TRT01PN -1 1
           TRT01PN*AVISITN 0 -1 0 0 1 / CL LOWER LOWERTAILED;
  ESTIMATE 'TRT S - P ON DAY 84' TRT01PN -1 1
           TRT01PN*AVISITN 0 0 -1 0 0 1 / CL LOWER LOWERTAILED;
  ODS OUTPUT PARAMETERESTIMATES=PESTIMATES;
  RUN;
/*First, sort the data of estimates by visit (variable "LABEL") */
PROC SORT DATA=PESTIMATES; BY LABEL; RUN;

/*Step 4: Combining estimates from each imputed data set */
PROC MIANALYZE DATA=PESTIMATES;
  MODELEFFECTS ESTIMATE;
  STDERR STDERR;
  BY LABEL;
  ODS OUTPUT PARAMETERESTIMATES=MIPARM;
```

```
RUN;

DATA MIPARM;
  SET MIPARM;
  SHIFT= &SJ;
RUN;

/*----- Output multiple imputation results -----*/
DATA &OUTPARMS;
  SET &OUTPARMS MIPARM;
RUN;

%END;
%MEND MIPARMS;

/*Assume that the tipping point for the shift parameter that reverses the
study conclusion is between 0 and 100. The following statement performs
multiple imputation analysis for each of the shift parameters 0,10,20,30,...,
100.*/

ODS LISTING CLOSE;
%MIPARMS (DATA=XXXX, SMIN=0, SMAX=100, SINC=10, OUTPARMS=PARMS1);

/* Step 5: Finding Tipping Point for Shift Parameter between 0 and 100 such
that p-value is less than 0.05, below is an example for a tipping point for
the shift parameter between 40 and 50.

For a two-sided Type I error level of 0.05, the tipping point for the shift
parameter is greater than 40. The following statement performs multiple
imputation analysis for shift parameters 40, 41, ..., 50*/

%MIPARMS (DATA=XXXX, SMIN=40, SMAX=50, SINC=1, OUTPARMS=PARM2);

/*The following statements display the p-values that are associated with the
shift parameters.*/

PROC PRINT LABEL DATA=PARM2;
  VAR SHIFT PROBT;
  TITLE 'P-VALUES FOR SHIFT PARAMETERS';
  LABEL PROBT='PR > |T|';
  FORMAT PROBT 8.4;
RUN;
```

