## 11.0 APPENDICES

### APPENDIX A: SAS SAMPLE CODES

A sample of the SAS code for MMRM analysis is provided as below:

```
/*GENERATE LOG-TRANSFORMED COUGH FREQUENCY FIRST*/

PROC MIXED DATA=LOGEFF METHOD=REML;
CLASS TRT01PN USUBJID AVISITN COUNTRY SEX;
MODEL LCHG = TRT01PN AVISITN COUNTRY SEX TRT01PN*AVISITN LBASE / DDFM=KR;
/*LCHG AND LBASE ARE BASED ON THE LOG-TRANSFORMED COUGH FREQUENCY*/
REPEATED / SUBJECT=USUBJID (TRT01PN) TYPE=UN;
LSMEANS TRT01PN*AVISITN / CL PDIFF;
  ESTIMATE 'TRT S - P ON DAY 28' TRT01PN -1 1
           TRT01PN*AVISITN -1 0 0 1 / CL LOWER LOWERTAILED;
  ESTIMATE 'TRT S - P ON DAY 56' TRT01PN -1 1
           TRT01PN*AVISITN 0 -1 0 0 1 / CL LOWER LOWERTAILED;
  ESTIMATE 'TRT S - P ON DAY 84' TRT01PN -1 1
           TRT01PN*AVISITN 0 0 -1 0 0 1 / CL LOWER LOWERTAILED;

RUN;
```

Where TRT01PN = planned treatment group in numeric (**1 = placebo, 2 = serlopitant 5 mg**); AVISITN = time point (i.e. Day 28, Day 56, and Day 84); COUNTRY (USA, UK); SEX (Female, Male); TRT01PN\*AVISITN = treatment by visit interaction; CHG = hourly cough frequency (on the log scale) - BASE (on the log scale); BASE = baseline hourly cough frequency (on the log scale); TYPE=UN specifies unstructured covariance matrix structure; METHOD=REML specifies the estimation method (REML is the default method); and DDFM=KR requests the Kenward-Roger method for the covariance matrix of the fixed-effect parameter estimates and denominator degrees of freedom for t and F tests.

A sample of the SAS code for ANOVA analysis of ranked 24-hour cough frequency at Week 12 (Day 84) is provided as below:

```
PROC RANK DATA= ADCF OUT=W12_RANK;
  WHERE AVISIT=7;
  RANKS CHG_RANK;
  VAR CHG; /*CHG AND BASE ARE BASED ON THE LOG-TRANSFORMED COUGH FREQUENCY*/
RUN;

PROC MIXED DATA=W12_RANK METHOD=REML;
CLASS TRT01PN USUBJID COUNTRY SEX;
MODEL CHG_RANK = TRT01PN COUNTRY SEX BASE / DDFM=KR;
/*CHG AND BASE ARE BASED ON THE LOG-TRANSFORMED COUGH FREQUENCY*/
LSMEANS TRT01PN / CL PDIFF;
  ESTIMATE 'TRT S - P ON DAY 84' TRT01PN -1 1
           / CL LOWER LOWERTAILED;

RUN;
```

A sample of the SAS code for CMH and M&H is provided as below:

SAS PROC FREQ procedure will be used. CRIT1FN is the response variable = '1' (i.e. non-responder as the reference level).

```
PROC SORT DATA=ADAMDATA.ADCF OUT=ADCF;  
BY USUBJID AVISITN;  
WHERE PARAMCD=' XXXXX' AND DTYPE='' AND AVISITN = x;  
RUN;
```

```
/*Treatment comparison using stratified CMH*/  
PROC FREQ DATA=ADCF;  

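### SAP Appendix A uses two incompatible treatment codings: under its only declared key, the tipping-point shift falls on placebo and copy-reference has no reference arm

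*SAP*

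**What the plan says.** The prose is clear. SAP 9.6.5 builds the copy-reference imputation model from the control group and applies the tipping-point shifts to imputed values in the active arm. It points to Appendix A for the code of both analyses.

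Appendix A declares one key for `TRT01PN`, under the MMRM code: "1 = placebo, 2 = serlopitant 5 mg". No recode appears anywhere, and both imputation blocks carry a comment to use the numeric `TRT01PN`.

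- **Copy-reference block.** The reference is "MODELOBS = (TRT01PN = '0", with the comment "Control=Placebo".
- **Tipping-point block.** The shift is "MNAR ADJUST( AVAL3 / SHIFT=&SJ ADJUSTOBS=(TRT01PN ='1", and the statements for the other two visits select the same level. The comment on this step begins "Impute all visits under MAR first, then apply delta adjustments at".
- **Data sets.** Copy-reference Step 2 is "PROC MI DATA=MONO SEED=14823 NIMPUTE=1 OUT=OUTM1". Tipping-point Step 1 writes `MONO`, but its Step 2 is "PROC MI DATA=OUTM1 SEED=14823 NIMPUTE=1 OUT=OUTM2". It is followed by "PROC SORT DATA =OUTM1; BY _IMPUTATION_ TRT01PN USUBJID BASE; RUN", although the MMRM then analyses `OUTM2`.
- **Criterion.** Step 5 describes a two-sided 0.05 level and prints a two-sided p-value. SAP 8.7 tests at one-sided 0.05.

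**The concern.** The two imputation blocks match SAP 9.6.5 only if placebo is 0 and serlopitant is 1. No key declares that coding, and it conflicts with the one that is declared.

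The error can pass unnoticed. The MMRM contrast puts -1 on the first level and +1 on the second, so it gives serlopitant minus placebo under either coding. A shift on the wrong arm would run and print normal-looking output. Because it penalises placebo, finding no tipping point would read as robustness.

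The code matters although it is a sample. Protocol 8.9.2.1 defers the technical details to the SAP, and the shift grid, seed and number of imputations appear only in Appendix A. SAP 9.6.2.1 relies on the sensitivity analyses of 9.6.5 to assess the missing-at-random assumption, with 15% dropout expected (SAP 8.2).

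**Working it through.** **1. Which subjects each statement selects (85 per arm)**

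| Block | Level in code | Arm intended | Under declared 1/2 key | Under undeclared 0/1 coding |
|---|---|---|---|---|
| MMRM contrast | first -1, second +1 | serlopitant minus placebo | as intended | as intended |
| Copy-reference `MODELOBS` | 0 | placebo | nobody (0 of 170) | placebo |
| Tipping-point `ADJUSTOBS`, three visits | 1 | serlopitant | placebo (85; serlopitant 0) | serlopitant |

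**2. What happens when the tipping-point code is run**

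- *Declared key, Step 2 repaired to read `MONO`:* the shift falls on placebo.
- *Run literally:* Step 2 has no input, or reads the copy-reference output. If that output is complete, no missing value is left to shift at any of the (100 - 0)/10 + 1 = 11 grid values.
- *Data coded 0/1:* the arms are right, but the declared key does not describe these data and the `OUTM1` fault remains.

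**3. Direction in the first case**

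SAP 9.6.5 imputes before the log transformation, so the shift is in coughs per hour. A shift d ≥ 0 on an imputed placebo value y gives log(y + d) ≥ log(y). The placebo log mean rises, and the ratio exp(serlopitant - placebo) falls.

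**4. Size in the first case**

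Inputs from SAP 8.2: ratio 0.75, CV 0.64, 15% dropout, 85 per arm. Log SD = sqrt(ln(1 + 0.64²)) = 0.586. This SD reproduces the plan's sample size: 72 per arm gives t-test power 0.901 at one-sided 0.05, and 72/0.85 = 84.7, so 85 per arm and 170 in total. Missing at Day 84: 0.15 × 85 = 12.75, so 13 per arm, 6 of them from Day 56.

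Assumed: median baseline 10, 20 or 40 coughs/h; log correlation 0.3 to 0.7; missingness at random; imputed values below 0.1 set to 0.1. The SAP 8.6 subgroup cut at 10/h and the awake rate of about 20/h upward in Protocol 1.1 guided the baselines.

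Method: raw-scale regression imputation, 10 imputations, the planned MMRM on log change, Rubin's rules. Runs: 3 baselines × 3 correlations × 2 ways of applying the shift (after imputation under MAR, or fed forward) × 120 trials = 2,160.

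| Criterion | Significant at zero shift | Tipped, placebo shifted | Tipped, serlopitant shifted |
|---|---|---|---|
| One-sided 0.05 | 1,779 | 0 | 1,751 (98%) |
| Two-sided 0.05 (Step 5) | 1,492 | 0 | 1,481 |

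With placebo shifted, the highest one-sided p was 0.029 and the mean ratio at +100 was 0.49 to 0.58. With serlopitant shifted, the median one-sided p passed 0.05 at a shift of about 5-10 (baseline 10/h), 10-20 (20/h) and 10-50 (40/h).

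Example at 20/h, correlation 0.7, shift after imputation (ratio, median one-sided p):

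| Shift | Placebo shifted | Serlopitant shifted |
|---|---|---|
| 0 | 0.724, 0.0038 | 0.724, 0.0038 |
| +10 | 0.666 | 0.816, 0.017 |
| +20 | 0.635 | 0.868, 0.074 |
| +100 | 0.538, below 0.0001 | not tabulated |

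With 3 to 21 of 85 missing per arm, equal or unequal (correlation 0.5, 900 trials), 726 were significant. None tipped with placebo shifted (highest p 0.040); 432 (60%) tipped with serlopitant shifted.

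A simpler single-visit simulation (correlation 0.6, baseline 20/h) agreed in direction. From 0.732 at zero shift, the ratio went to 0.530 at +100 on placebo and to 1.087 at +100 on serlopitant.

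**5. Limit of the direction claim**

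A shift on a few subjects also inflates the variance. For a constant log shift on k of 85 placebo subjects, the two-sample t tends to sqrt(85k/(85 - k)) = 1.01, 1.43, 1.76 and 3.92 for k = 1, 2, 3 and 13, against a critical 1.65. With only one or two subjects missing, an extreme placebo shift could therefore tip the result.

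**The case against.** The strongest reply is that the prose is right, the code is labelled a sample and contains placeholders, and a programmer would follow the text. The two imputation blocks agree with each other, and the comment shows which arm is meant. The declared key sits beside the MMRM code, so it could be right for that data set while the imputation file is coded 0/1. An empty reference arm should alert someone, as should an effect that grows while the penalty rises. All of this limits the severity. It does not remove the contradiction: the prose gives no level codes, Appendix A gives two sets, and no recode is stated.

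The literal-run case is also open to challenge. Under the declared key the copy-reference step may never complete `OUTM1`. If `OUTM1` has been transposed to long format, the tipping-point step would probably fail visibly. That is fair, and SAS behaviour was not tested. In none of these outcomes is the serlopitant arm stressed.

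On the simulation, only 1,779 of 2,160 trials (82%) were significant at zero shift, below what an analysis of the observed data would give. The tipping values therefore partly reflect raw-scale imputation and the 0.1 floor. Raw-scale imputation is the SAP's own rule; the floor is my assumption. The tipping values are illustrative, and the contradiction does not rest on them.

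**Conclusion.** The concern holds. The declared key and the two imputation blocks cannot all be right. Under the declared key, the code contradicts SAP 9.6.5 in both missing-not-at-random analyses. The copy-reference fault would probably be noticed. The tipping-point fault, once the input name is repaired, could run silently and favour serlopitant.

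The simulation sizes only that repaired case, on the 0 to 100 grid. The tipping value depends on the assumed baseline, correlation and missingness; the direction did not change in any setting tried. This is a simulation result, not a general proof.

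The two-sided wording is a separate inconsistency and is conservative. Scope is limited to non-gating sensitivity analyses of 24-hour and awake cough frequency. The primary MMRM, the testing hierarchy and the pattern-mixture approximation are untouched. It should be fixed, but it does not threaten the primary result.

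**What to change.** Use one declared coding in every block of SAP Appendix A:

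- Under the existing key, set `MODELOBS` to level 1 in the copy-reference step and `ADJUSTOBS` to level 2 in all three tipping-point statements. If the data will be coded 0/1, correct the key instead.
- Make tipping-point Step 2 read `MONO`, and sort `OUTM2`.
- Judge and print the tipping point at one-sided 0.05. Derive the one-sided p-value after pooling, because only the estimate and its standard error reach `PROC MIANALYZE`.
- Add a programming check that the estimate moves against serlopitant as the shift rises.

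The cost is a few lines of the SAP before database lock, with no change to data collection or trial conduct.
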